**Discussion of Inclusion/Exclusion Issues.** Most antipsychotics and antidepressants are thought to lower seizure threshold [21] and this may prompt questions on the safety of administering rTMS to individuals taking these medications. The best available evidence suggests that these agents likely do not significantly increase the risk of rTMS induced seizures. A review of the effects of various psychoactive agents, including antidepressants and antipsychotics [26], revealed that these agents in general do not affect motor threshold, which can be taken as a proxy measure for an agent's effect on cortical excitability, and hence a mediator of seizure potential. A recent review of TMS administered to individuals with schizophrenia in the context of on going antipsychotic treatment concluded that TMS is safe to administer in this population [27]. However, due to the particularly higher seizure risks associated with a few psychotropic agents [21], we will exclude subjects taking these agents. A recent review of TMS for the treatment of PTSD concluded that this treatment is well tolerated [28], suggesting that

PTSD or history of psychological trauma does not likely represent increased risk for adverse events. Therefore, history of trauma will not be an exclusionary factor.

**Cognitive Task:** We will administer a visual delayed response WM paradigm as a measure of cognitive function (see Fig. 4). We and others have previously published studies using similar WM paradigms [29] that have revealed robust performance deficits in schizophrenia compared to healthy control subjects with p values ranging between .001-.002 and effect sizes  $\sim 1.1$ . This task will be administered at baseline and post treatment to quantify

changes in cognition resulting from rTMS. Subjects will be presented with cue stimuli, and after a delay, a probe stimulus will be presented. At this point the subject is to determine if the probe matches one of the cue images. Match probability will be 50%. Trial duration will be 6 sec, with a variable inter-trial interval (1000–2000 ms). Grey scale fractal images were selected for the task because these stimuli are affectively neutral and less prone to verbal encoding compared to most other types of visual stimuli. This feature will discourage variable or shifting encoding strategies across individuals, groups and testing sessions,

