**rTMS Treatment:** The rTMS treatment will closely follow that of the Barr et al. study [9], which documented significant improvement in WM performance with rTMS applied to the DLPFC. All rTMS treatments will be administered at the VA Palo Alto Health Care System (VAPAHCS), where several groups are conducting rTMS studies for other neuropsychiatric conditions, including a VA Co-op study on depression led by [name], one of the collaborators on this study. rTMS will be administered on a MagVenture MagPro R30 unit. Subjects with schizophrenia will receive 20 treatments of rTMS occurring once a day, 5 days a week for 4 weeks, to DLPFC (alternating sessions between left and right hemispheres) at 20 Hz (non-patterned), at 90% resting motor threshold for 25 trains, 30 pulses/train, inter-train interval of 30 sec (750 pulses/hemisphere, a total of 1500 pulses/session/day) in accordance with published safety guidelines [42]. Total duration of daily TMS sessions will be ~50 min. The resting motor threshold will be defined as the lowest intensity that produces a motor evoked potential (measured by EMG of non-dominant abductor pollicis brevis) of at least 50 mV in 50% of the trials. Trained physicians or RNs will administer rTMS blinded to treatment condition, to which subjects will be randomized by software contained in the TMS system. rTMS stimulation coils have a built-in position sensor that ensures that the correct (active or sham) side of the coil faces towards the patient's head. If the coil position is wrong, the operator will get a "Flip Coil" prompt, while maintaining the blind. Blinding will be further facilitated by the delivery of white noise during stimulation to mask the characteristic sounds associated with rTMS, as well as low voltage electrical stimulation of the scalp designed to mimic skin surface stimulation that sometimes occurs with active rTMS administration.

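### The resting motor threshold, on which every subject's stimulation intensity depends, is defined by a 50 mV EMG response that appears unreachable; the printed unit needs checking and, if confirmed, correcting

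*Combined protocol and SAP*

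**What the plan says.** Under Research Design and Methods, the rTMS Treatment paragraph gives the stimulation "at 90% resting motor threshold for 25 trains, 30 pulses/train, inter-train interval of 30 sec". It then says how the threshold is found, and the rule has three parts. The quantity sought is stated as follows: "The resting motor threshold will be defined as the lowest intensity that produces a motor evoked potential". To count, the response has to reach a size "of at least 50 mV in 50% of the trials". The recording site is a thumb muscle, with the response "measured by EMG of non-dominant abductor pollicis brevis".

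The same paragraph says that treatment will stay close to the published randomized study of rTMS and working memory (reference [9]) and will accord with published safety guidelines (reference [42]). It reproduces no threshold criterion from either source.

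Motor threshold appears in one other place, the Discussion of Inclusion/Exclusion Issues. There the plan argues that psychoactive drugs in general "do not affect motor threshold, which can be taken as a proxy measure for an agent's effect on cortical excitability". That passage gives no amplitude and no unit.

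**The concern.** A threshold rule looks for the weakest stimulus that produces a response about half the time, so the response it asks for should be small. A 50 mV response recorded by EMG from a small hand muscle looks larger than such a muscle can produce at all. If so, the search described in the protocol has no end point.

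RMT is the only scale on which intensity is expressed. If the written rule cannot be met, the intensity cannot be derived from the protocol. An operator would have to apply a criterion that is not written down, and operators could differ in what they apply. The intensity delivered would then not be traceable to the protocol. That matters in a pilot with 12 subjects on active treatment, whose declared purpose is to learn the direction and size of the effect for use in planning larger studies. Those estimates are only as interpretable as the intensity that produced them.

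**Working it through.** **Inputs from the document (rTMS Treatment paragraph)**
- Intensity = 0.90 × RMT.
- RMT = lowest intensity at which the evoked response is at least 50 mV in 50% of trials.
- Recording: EMG of the non-dominant abductor pollicis brevis.
- Dose structure: 25 trains of 30 pulses; "750 pulses/hemisphere, a total of 1500 pulses/session/day"; once a day, 5 days a week, 4 weeks, 20 treatments.

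**Input that the document does not give (assumption)**
- The largest EMG response of a small hand muscle, M, is a few millivolts and at most about 20 mV. The range used is 5 to 20 mV.

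**Step 1. Reproduce the plan's own arithmetic.**
- 25 × 30 = 750 pulses per hemisphere, as stated.
- 2 × 750 = 1500 pulses per day, as stated.
- 5 × 4 = 20 treatments, as stated.

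None of these uses the response criterion. The 50 mV figure is a definition with no inputs, so there is no calculation to reproduce.

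**Step 2. Compare the criterion with the assumed maximum.** Ratio = 50 mV / M.

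| Assumed maximum M | 50 / M |
|---|---|
| 5 mV | 10 |
| 10 mV | 5 |
| 20 mV | 2.5 |

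The ratio is above 1 across the range. The criterion becomes attainable only if M is at least 50 mV, which is 2.5 times the top of the assumed range. The conclusion therefore does not hang on one chosen value of M.

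**Step 3. Follow the rule through.** If no output setting gives a response of 50 mV, no intensity satisfies the definition, a lowest such intensity does not exist, and 0.90 × RMT is undefined.

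**Step 4. Look for a fallback.** The document offers no second definition of RMT, no expected range of response amplitudes and no EMG recording range. The Discussion of Inclusion/Exclusion Issues mentions motor threshold without a figure. Nothing else in the text resolves the question.

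**The case against.** **No internal contradiction.** No other passage conflicts with 50 mV. The objection rests on an assumption about muscle responses, not on the plan's own figures. This stands: it makes the point conditional, and the assumption has to be stated openly.

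**Possible reading error.** The point turns on one unit prefix in text read from PDF by a program. Other Greek symbols survived the extraction, namely the ohm sign in the EEG paragraph and the delta signs in the Statistical Analysis section. That makes a misread character less likely but does not exclude it. The page has to be looked at first.

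**Trained staff and outside references.** Trained physicians or nurses give the treatment, it is modelled on a published study and guidelines, and the Preliminary Studies section reports an earlier rTMS study in which 27 subjects completed with no adverse outcomes. This makes an unnoticed problem in practice less likely. It does not repair the written rule, because staff who recognise the problem would still be working to a criterion that the protocol does not contain.

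**Stronger readings that the documents do not support.**
- A reader might infer that subjects would be stimulated far above the intended intensity, because an operator would raise the output to the device maximum and take 90% of that. This does not follow: if the criterion is never met, there is no RMT and no 90% figure.
- A reader might infer that the unit is wrong by a factor of exactly 1000. The factor is the ratio of millivolt to microvolt, but the document does not say which unit was intended.
- A reader might infer a safety contradiction from the description of motor threshold as a proxy for excitability. That sentence concerns the effect of concomitant drugs, not how the threshold is measured.

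**Conclusion.** The point holds in conditional form. The only operational definition of RMT, and so the only basis for each subject's intensity, asks for a response that is 2.5 to 10 times the largest obtainable one if that maximum is 5 to 20 mV. Read literally, it then yields no RMT and no stimulation intensity.

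Two conditions carry this: that the source page does read mV, and that the maximal response is well below 50 mV. The first can be settled by looking at the page. The second is an assumption, though it would have to be wrong by a factor of 2.5 at its upper end for the rule to work.

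This is an implausible unit in a working definition, not a failure of the plan's arithmetic. It deserves correction because the trial relies on the figure for every subject. The sample size, alpha level and analyses are unaffected.

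**What to change.** 1. Check the unit on the source page. If it shows a different symbol, the point lapses.
2. If it reads mV, reconcile the criterion in the rTMS Treatment paragraph with the protocol of the study it says it follows (reference [9]), the cited safety guidelines (reference [42]) and the site's EMG procedure. Correct the unit so that an RMT can be obtained and the 90% intensity follows from it. The sponsor and investigators must settle the value; none is proposed here.

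The cost is a check of one page and, if needed, a correction to one unit in the protocol. It adds no procedure, visit or subject.

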## Statistical Analysis

**Hypothesis Testing, Aim 1 - Subjects receiving rTMS will show improvements in a) WM performance, and b) occupational/role functioning compared to subjects receiving sham treatment:** Change scores (post-TMS vs. pre-TMS) for WM performance accuracy ( $\Delta$ WM Acc) and Global Functioning ( $\Delta$ GF) will serve as dependent measures for testing the hypothesis that rTMS improves cognition and functioning, respectively. The hypothesis will be supported if we find greater  $\Delta$ WM or  $\Delta$ GF in the active compared to the sham rTMS treated groups. We will use independent samples t-tests and two-sided tests for significance testing, with an alpha level of 0.05. However, given the limited scope of the SPiRE award, our primary goal is not on finding statistically significant differences but rather on determining the directionality of changes and the effect sizes of treatment effects. These data will be critical for determining if there is preliminary evidence that could support proposals for future larger scale studies.

**Hypothesis Testing, Aim 2 - Subjects receiving active treatment compared to those receiving sham treatment will show a) increased cognition associated gamma oscillation power, and b) an associated improvement in task performance:** Hypothesis 2 will be supported if we find significantly greater  $\Delta$ gamma in the active rTMS compared to the sham treated group. In addition, in the active rTMS treated group, we will conduct Pearson's bivariate correlation between  $\Delta$ gamma and  $\Delta$ WM. A positive correlation between these variables will support the hypothesis that rTMS improves cognition by increasing gamma oscillations. We will explore the possibility that pre-treatment gamma predicts rTMS responsiveness. We will evaluate this possibility by conducting a median split analysis in which subjects will be binned by their baseline gamma levels. We predict that those in the lower half of the distribution will show higher  $\Delta$ gamma and  $\Delta$ WM.

**Intent-to-treat:** We will conduct a modified ITT analysis for hypothesis testing. We will use a modified ITT, which includes only subjects with outcome data, e.g. cognitive performance and EEG at the end of treatment [43], since good proxy measures cannot be imputed. To minimize missing data, we will acquire cognitive performance and EEG within one week of their last TMS session, including those intending to drop out. We will supplement this analysis with a per protocol analysis in which only subjects who completed all TMS treatments will be compared. This is done to determine, in a proof of concept manner, if TMS has the capacity to improve cognition in schizophrenia. We will include a careful examination of whether bias has been introduced due to dropout by determining if there is greater dropout in the treatment group and if significant differences exist in

major demographic and clinical variables of individuals who have dropped out compared to those who have not. We will correct for any significant differences using covariates in our statistical models.

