Gamma Oscillation as a Potential Marker of rTMS Effects on the DLPFC. A better understanding of neural mechanisms holds the potential to yield clinically useful biomarkers predictive of rTMS treatment response. The availability of predictors would be useful because psychiatric treatments typically are ineffective for a substantial proportion of subjects and predictors would promote the judicious use of treatments so that only those individuals most likely to benefit are exposed to the risks and costs of treatment. The emerging literature on rTMS suggests that this treatment modality also suffer from this limitation. In the study by Barr et al., a substantial proportion of subjects did not benefit from TMS. In fact, a close examination of their data indicates that ~31.5% of subjects experienced lower performance post treatment compared to pre treatment. Although rTMS is generally considered safe, it, nonetheless, is a procedure that alters function of the targeted brain tissue. Thus, an additional goal of this proposal is to obtain preliminary support for pretreatment (baseline) gamma activity as a predictor of rTMS remediation of cognitive deficits in schizophrenia. We will evaluate the potential utility of gamma oscillations as a response predictor by testing whether baseline levels of gamma is associated post-treatment improvements in cognitive performance.

[figure not shown]
Innovation. The proposal represents an innovative approach to new treatment development for cognitive deficits associated with schizophrenia. We are not aware of any studies that have applied rTMS to Veterans for this purpose. The use of EEG frequency analysis to gauge the neurophysiologic effects of rTMS represents a novel combination of sophisticated methods. This combination also represents a mechanism-based approach to treatment development. Moreover, this approach promises to yield early indications for clinically relevant predictive information. We are not aware any studies that have examined potential predictors of rTMS efficacy to remediate cognitive deficits in schizophrenia. With the successful completion of this project, there is the potential translate our findings towards personalized treatment for Veterans suffering from cognitive deficits in schizophrenia.

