### Subjects

Table 1. Experimental Design

Clinical Assessment	Phase			
	Baseline	Randomization	Treatment	Post-treatment
	Week 1	End of Week 1	Wk 2 → Wk 6	Wk 7
Telephone Screen	WM Task		rTMS	WM Task

[figure not shown]

Figure 2. Scalp topography of control-related gamma oscillation power deficits in schizophrenia group compared to a healthy comparison group during the delay period of cognitive control task. Right frontal EEG leads show the most prominent deficits in schizophrenia. Left and right panels show superior and right lateral views respectively. From Minzenberg et al. [17].

Office Evaluations (SCID)	EEG Functional Status	[rTMS, Sham]	Sham	EEG Functional Status
---------------------------	-----------------------	--------------	------	-----------------------

A total of 24 subjects (12 rTMS and 12 sham) with SZ or SAD between the ages of 18 and 55 will be studied. Veterans will be recruited from a variety of sources including VAPHCS mental health clinics. We will consult with our system's Office of Data Analytics to identify potential subjects. We have already identified 366 veterans within the VAPAHCS population meeting the inclusion/exclusion criteria. We will work with this office to identify these veterans' VA clinicians who will assist in recruitment efforts. The study will be open to both men and women, regardless of race and ethnic origin. Details of demographics of the local VA population can be found in pg. 1 of the Human Subjects section.

Table 2. Inclusion and Exclusion Criteria

Exclusion Criteria	Inclusion Criteria
1) Pregnant or lactating female	1) Age 18-55 years
2) History of prior adverse reaction to TMS	2) SCID confirmed diagnosis of SZ or SAD
3) On medications known to significantly lower seizure threshold, e.g. clozapine, chlorpromazine, bupropion, clomipramine [21]	3) Stable medication regimen (no change in dose or agents within the 4 weeks prior to study entry and throughout the duration of the study)
4) History of seizures or conditions known to substantially increase risk for seizures	4) Stable social environment and housing to enable regular attendance at clinic visits
7) Implants or medical devices incompatible with TMS	5) Ability to undergo cognitive testing, EEG scans and rTMS
8) Acute or unstable chronic illness that would affect participation or compliance with study procedures, e.g. unstable angina	6) IQ > 80 (WASI full scale score)

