which, if present, could significantly diminish our ability to detect true treatment effects. There will be a control condition in addition to the WM condition. The trial structure and stimuli of the control trials will be identical to those of the WM trials but subjects will be instructed to passively view the stimuli and register a response with a button press when the probe image appears. Control trials will facilitate more accurate assessment of WM associated gamma oscillations by allowing the investigators to subtract out non-WM associated EEG signals. This will also minimize inter-subject differences that may confound the detection of true experimental effects. There will be 40 trials in each condition and trials will be blocked by condition, with 10 trials/block and a brief rest period between blocks. The condition for the upcoming block will be indicated by text and the condition block order will be pseudorandomized.

**Assessment of Functional Status:** To assess the effect of rTMS on real world functioning, we will utilize the Global Functioning: Role Scale (GF). This scale is a well-validated measure of occupational/role functioning in individuals with schizophrenia and related conditions [30, 31]. It is a brief easy to apply 6-item scale that avoids confounding functioning with psychiatric symptoms, a problem found in other commonly used scales such as the Global Assessment of Function. We recently assessed the reliability of this scale in our group. Two raters independently applied this scale on 10 subjects with schizophrenia and these ratings yielded an intraclass correlation = 0.88.

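### Aim 1 tests unadjusted change scores although both baselines are collected; ANCOVA on baseline would usually be more precise, at a cost of at most about 5% in variance

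*Combined protocol and SAP*

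**What the plan says.** The dependent measures for Aim 1 are given as "Change scores (post-TMS vs. pre-TMS) for WM performance accuracy" and the corresponding change in GF. The test is stated as "We will use independent samples t-tests and two-sided tests for significance testing, with an alpha level of 0.05". The same paragraph puts estimation ahead of significance: the main goal is "determining the directionality of changes and the effect sizes of treatment effects", to support larger studies.

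Both baselines are available. On the WM task, the Cognitive Task section says "This task will be administered at baseline and post treatment to quantify" change. Table 1 lists "EEG Functional Status" at baseline and again after treatment. The planned sample is 24, 12 per arm.

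The only mention of covariates is under Intent-to-treat. It applies only if the dropout examination finds significant differences, so it does not provide for adjustment by baseline outcome.

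**The concern.** A change score fixes the slope of post on pre at 1. When the true slope is lower, as it is when measurement noise pulls extreme baselines back towards the mean, subtracting the whole baseline adds noise and over-corrects for chance imbalance. ANCOVA estimates the slope from the data.

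At most 12 subjects per arm will contribute, so chance baseline imbalance may be sizeable. The product of the trial is an effect estimate for planning the next study. An avoidable loss of precision bears directly on that, and the data needed to avoid it are already being collected.

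**Working it through.** **Inputs.** From the documents: n = 12 per arm, two-sided alpha 0.05, 40 WM trials per condition. Assumed, because the documents do not give them: the pre-post correlation rho and the ratio k = SD_post/SD_pre. The plan states no precision or power figure for Aim 1, so there is nothing to reproduce first.

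**Formulas** (common slope rho·k, normally distributed baseline):

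- Var(change) = s_pre² (1 + k² − 2k·rho) × 2/n, which equals s_pre² [k²(1 − rho²) + (1 − rho·k)²] × 2/n
- Var(ANCOVA) = s_pre² k²(1 − rho²) × 2/n × F, with F = 1 + 1/(2n − 4) = 1 + 1/20 = 1.05

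The second form of Var(change) contains the ANCOVA residual variance plus a squared term that cannot be negative. The ratio ANCOVA/change therefore never exceeds F: 1.05 at 12 per arm, 1.0625 at 10, 1.083 at 8.

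**Variance ratio, ANCOVA to change score, 12 per arm**

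| k | rho 0.3 | 0.5 | 0.7 | 0.8 | 0.9 | 0.95 |
|---|---|---|---|---|---|---|
| 0.8 | 0.53 | 0.60 | 0.66 | 0.67 | 0.64 | 0.55 |
| 0.9 | 0.61 | 0.70 | 0.79 | 0.83 | 0.85 | 0.83 |
| 1.0 | 0.68 | 0.79 | 0.89 | 0.945 | 1.00 | 1.02 |
| 1.1 | 0.75 | 0.86 | 0.97 | 1.02 | 1.05 | 1.03 |
| 1.2 | 0.80 | 0.91 | 1.01 | 1.05 | 1.03 | 0.92 |

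Example, k = 1 and rho = 0.5: 1.05 × 0.75 / 1.00 = 0.7875, equivalent to 12/0.7875 = 15.2 per arm under the change-score analysis. At k = 1.1 and 1.2 the equivalents are 12/0.858 = 14.0 and 12/0.9145 = 13.1.

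**Where ANCOVA loses.** k = 1: rho above 0.905. k = 1.1: rho 0.77 to 0.97. k = 1.2: rho 0.67 to 0.92, that is, slopes of about 0.80 to 1.10. k = 0.9 or 0.8: nowhere.

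**Extra spread in the active arm only**, unrelated to baseline (active post SD 1.12 or 1.20 times baseline): the ratio is 0.82 or 0.83 at rho 0.5, 0.92 or 0.93 at 0.7, and about 1.02 at 0.9.

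**Simulation** (100,000 runs per cell) reproduced the ratios to within 0.006, with type I error of 4.8% to 5.2% for both methods. Mean 95% CI half-width in baseline SDs, change score to ANCOVA:

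| k | rho 0.3 | 0.5 | 0.7 | 0.8 |
|---|---|---|---|---|
| 1.0 | 0.99 to 0.82 | 0.84 to 0.74 | 0.65 to 0.61 | 0.53 to 0.52 |
| 1.2 | 1.10 to 0.98 | 0.93 to 0.89 | 0.73 to 0.74 | 0.60 to 0.62 |

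**Chance imbalance.** A 1-SE baseline difference is sqrt(2/12) = 0.41 SD. It shifts the change-score estimate by (1 − rho·k) × 0.41: at k = 1, by 0.29, 0.20, 0.12 and 0.04 SD for rho 0.3, 0.5, 0.7 and 0.9.

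**WM accuracy.** Forty trials put a ceiling on rho. At an assumed mean accuracy of 75%, the average binomial error variance is (1875 − SD²)/40 squared percentage points, where SD is the assumed true between-subject SD. The ceiling is SD²/(SD² + error).

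| True SD (points) | Error variance | Ceiling on rho | Ratio at ceiling, k = 1.0 | k = 1.1 | k = 1.2 |
|---|---|---|---|---|---|
| 10 | 44.4 | 0.69 | 0.89 | 0.96 | 1.01 |
| 15 | 41.3 | 0.85 | 0.97 | 1.04 | 1.05 |
| 20 | 36.9 | 0.92 | 1.006 | 1.05 | 1.01 |

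These are upper limits on rho, since day-to-day variation and varied treatment response lower it. With equal SDs a lower rho always favours ANCOVA more.

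**GF.** No such ceiling can be derived. Table 2 requires "Stable social environment and housing to enable regular attendance at clinic visits", so role functioning may change little over the study and the slope may be near 1. The one reliability figure, "these ratings yielded an intraclass correlation = 0.88", comes from two raters and is not a test-retest value.

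**The case against.** The planned t-test is unbiased under randomisation, prespecified and two-sided. Choosing between two valid estimators can be called preference, especially when the deciding quantities are unknown and the range of ratios crosses 1. This stands in part: the size of the gain cannot be fixed from the documents, and at k = 1.2 an ordinary rho of 0.7 already gives a slight loss.

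The WM ceiling argument is favourable mainly when SDs are equal. At the ceiling itself, k = 1.1 gives a gain in one of three cases and k = 1.2 in none. That also stands. The Background remark that about "31.5% of subjects experienced lower performance post treatment compared to pre treatment" in the earlier rTMS study makes a wider post-treatment spread conceivable, but it does not determine the SD ratio. At rho 0.7 or above, the interval narrows little or not at all unless the post SD is the smaller one.

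Two further objections do not stand. First, moving Aim 1 to ANCOVA does not put it at odds with the change-score correlations of Aim 2: with baseline in the model, regressing the post score or the change score gives the same treatment coefficient. Second, the 5% bound assumes a normal baseline while GF is a short rating scale. Simulating rounded and floor-limited scores of that kind gave ratios no worse than the normal case: 0.76 to 0.78 at a latent correlation of 0.5, and about 1.00 to 1.01 at 0.95.

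**Conclusion.** The point holds as a recommended improvement in precision. The planned test is not wrong.

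The possible outcomes are lopsided. The loss is at most 5% of variance at 12 per arm. The gain is 21% at rho 0.5 with equal SDs, 14% at k = 1.1 and 9% at k = 1.2, and it is larger at lower rho or when the post SD is smaller than the baseline SD. ANCOVA fails to gain only when the slope rho·k is near 1, a zone that widens as the post SD grows. A gain is likelier for WM accuracy and may be nil for GF. All these figures depend on assumed rho and k, so confidence in the size is moderate. The direction of the advice does not depend on them, given the bounded loss and the plan's emphasis on estimation.

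**What to change.** For WM accuracy and GF, prespecify ANCOVA of the post-treatment score on arm plus the baseline of the same outcome, used whatever any significance test of baseline or dropout differences shows. Settle this before unblinding.

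Report the adjusted difference and the standardised effect with 95% CIs, and name the SD used to standardise. Also report the observed pre-post correlation and the pre and post SDs for each outcome; planners of a larger trial will need them and these documents do not supply them. Keep the change-score t-test as a sensitivity analysis. Aim 2 need not change.

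Cost: SAP wording, no new data, one residual degree of freedom (22 to 21) and, if the slope proves near 1, a variance loss of at most about 5% at 12 per arm.

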Impairments in Gamma Oscillations Hypothesized to Underlie Cognitive Deficits in Schizophrenia. A secondary goal of this study is to advance our understanding of the neural mechanism of cognitive deficits. Toward this goal, we will test the gamma oscillation hypothesis of cognitive deficits in schizophrenia. Gamma oscillations are high frequency (30-80 Hz) oscillations resulting from the synchronization of activity among neuronal populations during cognition and information processing [14, 15]. While the precise mechanisms for cognitive deficits in schizophrenia are likely complex, involving multiple systems and processes [10], several lines of evidence converge on the centrality of impaired gamma oscillations in this condition [11-13]. This evidence includes findings pointing to a reduction in GABAergic signaling in schizophrenia. GABA is the major inhibitory neurotransmitter in the brain and GABA signaling is thought to be critical for the synchronization of firing among populations of pyramidal neurons. One of the most important physiological consequences of deficits in GABA signaling and synchronization of neuronal activity in schizophrenia is the inability to generate oscillations in the gamma range during cognition [11]. Our group and others have reported consistent evidence that gamma oscillations are disturbed in schizophrenia [16-20] during a range of PFC-dependent higher-order cognitive processes, including WM. We will test our hypothesis by determining whether rTMS induces changes in the level

of cognition-evoked gamma oscillations measured by electroencephalography (EEG), and whether these changes are associated with improvements in cognitive performance.

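### Aim 2b reads a positive gamma–WM correlation in the active arm alone (at most 12 subjects, no interval or threshold) as support for a causal mechanism

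*Combined protocol and SAP*

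**What the plan says.** All references are to the combined protocol and SAP.

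- **Statistical Analysis, Aim 2.** The heading sets active against sham, with part b worded as "b) an associated improvement in task performance". Part a has a between-arm criterion: "Hypothesis 2 will be supported if we find significantly greater" gamma change in the active arm. For part b, "in the active rTMS treated group, we will conduct" a Pearson correlation of gamma change with WM change. The inference rule follows: "A positive correlation between these variables will support the hypothesis that rTMS improves cognition by increasing gamma oscillations". No sham-arm correlation is planned.
- **Statistical Analysis, Aim 1.** The section's only alpha is here: "We will use independent samples t-tests and two-sided tests for significance testing, with an alpha level of 0.05". The same paragraph puts the main emphasis on "determining the directionality of changes and the effect sizes of treatment effects".
- **Background and Significance.** Mechanism is introduced as secondary: "A secondary goal of this study is to advance our understanding of the neural mechanism of cognitive deficits". The question about gamma changes is put as an association, namely "whether these changes are associated with improvements in cognitive performance".
- **Subjects; Intent-to-treat.** There are 12 subjects per arm, and only those with outcome data are analysed. No dropout rate is given.
- **Overview of General Design; Table 1.** Both arms have the WM task with EEG before and after treatment.

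**The concern.** Three things come together in one sentence.

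1. Part b is headed as a comparison of arms, but the analysis uses one arm, although the sham subjects have the same measurements.
2. The Background asks about association; the analysis section concludes that rTMS works *by* increasing gamma.
3. The word positive is undefined. It may mean sign only, which fits the stated interest in direction, or significant at the two-sided 0.05 level given under Aim 1. No interval is promised on either reading.

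The causal step fails on both readings, because shared influences such as practice, alertness or EEG quality can move both change scores. The plan itself contains a further link. The EEG section drops error trials before gamma is computed, and half of all probes are matches. If some correct answers are guesses (my assumption), a subject whose accuracy improves has fewer guessed trials in the retained set. Measured gamma could then follow performance, rather than drive it.

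What is at stake is a mechanism statement that the data cannot bear, and that could enter the case for a larger trial.

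**Working it through.** The plan gives no power or precision figure for this correlation, so there is none to reproduce.

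**Inputs from the documents:** 12 subjects in the active arm and 12 in sham (Subjects); two-sided 0.05 (Aim 1); d = 0.92 for WM in an earlier rTMS study (Background). **Assumed, because not given:** gamma effect d of 0.5 or 0.92 (the latter borrowed from WM); within-arm correlation ρ from 0 to 0.5, equal in both arms; 10 active subjects with data as an example of loss.

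**Step 1: the correlation alone.** With true correlation zero, r > 0 has probability 0.50 by symmetry. For significance at n = 12 (10 df, t = 2.228), the critical value is t/√(df + t²) = 2.228/√(10 + 4.96) = 0.576. It is exceeded on the positive side with probability 0.025.

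**Step 2: precision.** The 95% CI is tanh(atanh r ± 1.96/√(n − 3)). For r = 0.30, atanh r = 0.310.
- n = 12: 0.310 ± 1.96/3 = 0.310 ± 0.653, giving -0.33 to 0.75.
- n = 10: 0.310 ± 1.96/√7 = 0.310 ± 0.741, giving -0.41 to 0.78.

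**Step 3: joint rates when the mechanism is false.** Suppose rTMS raises gamma but gamma does not drive WM, and the within-arm correlation comes from shared factors. The rates come from simulated bivariate normal data, 12 per arm, 400,000 trials per setting, with t-tests counted when significant in the favourable direction. Each cell runs from ρ = 0 to ρ = 0.5.

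| Conditions required | Assumed d | r > 0 | r significantly positive |
|---|---|---|---|
| Gamma test | 0.5 | 11–20% | 0.5–8% |
| Gamma test | 0.92 | 29–55% | 1–22% |
| Gamma and WM tests; rTMS has no WM effect | 0.5 or 0.92 (gamma) | 0.3–2.2% | under 1% |
| Gamma and WM tests; rTMS improves WM by another route | 0.5 (both) | 2–9% | 0.1–3% |
| Gamma and WM tests; rTMS improves WM by another route | 0.92 (both) | 17–39% | 1–15% |

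Hand check at ρ = 0 and d = 0.92: the two-sample t-test with 12 per arm has power 0.577. Gamma test and r > 0: 0.577 × 0.50 = 0.29. Adding the WM test at the same d: 0.577 × 0.577 × 0.50 = 0.17. Both agree with the table.

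**Step 4: can sham serve as a test?** The difference of two Fisher-transformed correlations has SE √(1/9 + 1/9) = 0.471, and 1.96 × 0.471 = 0.924. With sham r = 0, active r would have to exceed tanh(0.924) = 0.73 to differ at two-sided 0.05. A sham correlation is therefore context and cannot be used as a formal control.

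**The case against.** The best defence is that the plan claims only support, not proof. A positive correlation is what the gamma hypothesis predicts, so seeing one is weak evidence in its favour. It is also an addition to a randomised between-arm gamma test, and Aim 1 separately tests whether rTMS improves WM. If both tests are taken as implied and rTMS has no WM effect, the joint rate is at most 2.2%. The 0.05 level may be meant to cover the correlation; if not, a sign-based reading suits a pilot interested in direction. The control trials described under Cognitive Task also subtract EEG signal unrelated to WM, which removes some shared noise.

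Much of this stands, and it keeps the point minor. The 50% figure describes the correlation alone, not Aim 2 as a whole, and the joint rates rest on effect sizes that the documents do not give. But the sentence is not made conditional on the WM test. Even with both tests required, a WM benefit through another route leaves 17–39% on the sign reading at d = 0.92. An interest in effect sizes calls for an interval. Control-trial subtraction does not remove influences on WM-related gamma and WM accuracy together.

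**Conclusion.** The concern holds and is minor. The active-arm restriction, the absence of an interval or threshold, and the causal wording are all in the text. The precision figures need only n = 12 and the usual normal-theory approximations. The joint rates are illustrations over assumed gamma effects and correlations, and they depend on whether positive means sign or significance. The main conclusion does not depend on them: on either reading, a correlation in at most 12 subjects of one arm cannot show that gamma is the pathway. No primary result is affected.

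**What to change.** Keep the between-arm gamma test and the active-arm Pearson correlation. Replace the inference sentence with:

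> We will report the correlation between gamma change and WM change with a 95% CI in each arm. These are exploratory associations and will not by themselves be taken as evidence that rTMS improves cognition by increasing gamma.

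Do not require the association to be absent or weaker in sham. A real gamma-to-WM effect could appear in both arms, and 12 per arm cannot separate them. A pooled, arm-adjusted estimate may be added as a supplement with its common-slope assumption stated; it does not remove confounding.

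The cost is SAP wording only, since the sham EEG and WM data are already collected. The price is a more cautious mechanistic statement, and the per-arm correlations remain imprecise and open to confounding at this size.
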